5 INTRODUCTION

5.1 Rationale and Background

In this clinical study, the performance of the investigational [REDACTED] contact lens will be compared to the commercially available Biofinity contact lens in a parallel group design to demonstrate the safety and effectiveness of the [REDACTED] contact lens, worn daily [REDACTED]

[REDACTED] as compared to Biofinity contact lens, worn daily [REDACTED]
[REDACTED] The intended use of this contact lens is for vision correction. Therefore, the measurement of distance VA is planned as the primary effectiveness variable.

[REDACTED]

[REDACTED]

[REDACTED]

5.2 Purpose of the Study

The purpose of this clinical study is to demonstrate the safety and performance of the investigational [REDACTED] soft contact lens compared to the commercially available Biofinity soft contact lens when worn in a daily wear modality, by assessing visual acuity as the primary variable.

At the end of the study, a clinical study report will be prepared in accordance with applicable regulatory requirements and standards.

[REDACTED]

[REDACTED]

5.3 Risks and Benefits

Contact lenses may offer improved peripheral vision and the convenience of not wearing spectacles. Material properties and design characteristics of [REDACTED] contact lenses are features consistent with successful contact lens wear. Based upon nonclinical testing and documented rationale for applicability of test results, [REDACTED] contact lenses are assessed to be non-toxic and biocompatible for on-eye use.

In the US, Biofinity contact lenses have approved indications for use for both daily wear and extended wear for up to 6 continuous nights. Further details on any known potential risks and benefits can be found in the product package insert.

A summary of the known potential risks and benefits associated with [REDACTED] contact lenses can be found in the IB. [REDACTED]

[REDACTED]

[REDACTED]

In

[REDACTED]

[REDACTED]

[REDACTED]

Refer to the IB for additional information.

6 STUDY OBJECTIVES

6.1 Primary Objective(s)

Table 6–1 Primary Objective(s)

Objective(s)	Endpoint(s)
Demonstrate safety and effectiveness of [REDACTED] soft contact lens when worn for daily wear as compared to Biofinity soft contact lens.	Primary Effectiveness 
• Distance VA (Snellen)

6.2 Secondary Objective(s)

Not Applicable

6.4 Safety Objective(s)

Table 6–2 Safety Objective(s)

Objective(s)	Endpoint(s)
Duty of care and evaluation of safety profile of the investigational products.	AEs Biomicroscopy findings Device deficiencies

7 INVESTIGATIONAL PLAN

7.1 Study Design

This will be a prospective, randomized, [REDACTED] controlled, double-masked, parallel-group, daily wear clinical study.

This clinical study will engage approximately 8 clinic sites to enroll approximately 120 subjects with approximately 15 subjects per site.

Subjects will be expected to attend 6 office visits: Screening / Baseline / Dispense , Week 1 Follow-up, Week 2 Follow-up, Month 1 Follow-up, Month 2 Follow-up, and Month 3 Follow up/Exit. The total expected duration of participation for each subject is approximately 3 months in this daily wear study. Subjects will be randomized to wear either the test [REDACTED] contact lenses in both eyes or the control Biofinity contact lenses in both eyes.

[figure not shown]
Following randomization, study lenses will be dispensed to the subject [REDACTED]

[REDACTED]
[REDACTED]
[REDACTED]

Subjects will wear the lenses while awake in a daily wear modality. CLEAR CARE will be used for daily cleaning and disinfection. [REDACTED]

[REDACTED]
[REDACTED]

Figure 7-1 **Flowchart of Study Visits**

7.4 Rationale for Choice of Control Product

The Biofinity contact lens was chosen as the control product [REDACTED] to compare to [REDACTED] contact lens with regard to effectiveness and safety. Both the [REDACTED] contact lens and Biofinity contact lens are frequent replacement SiHy lenses and are to be prescribed for daily wear. The Biofinity contact lenses are indicated for the optical correction of refractive ametropia (myopia and hyperopia) in phakic or aphakic

persons with non-diseased eyes. [REDACTED]

[REDACTED]

7.5 Data Monitoring Committee

Not Applicable

8 STUDY POPULATION

The study population consists of adult male or female subjects (aged 18 or over), with non-diseased eyes, who require optical correction for refractive ametropia. [REDACTED]

[REDACTED]

The intended study population consists of volunteer subjects who are frequent replacement daily wear soft contact lens wearers, excluding Biofinity habitual wearers, who have at least 3 months of contact lens wearing experience, and who wear their habitual lenses at least 5 days per week and 8 hours per day. [REDACTED]

[REDACTED]

[REDACTED]

8.1 Inclusion Criteria

Written informed consent must be obtained before any study specific assessment is performed. Upon signing informed consent, the subject will be considered enrolled in the study.

Subjects eligible for inclusion in this study must fulfill **all** of the following criteria:

1. At least 18 years of age and be able to understand and sign an IRB/IEC approved Informed Consent form.
2. Willing and able to attend all scheduled study visits as required per protocol.
3. Successful wear of spherical daily wear frequent replacement soft contact lenses for distance correction in both eyes during the past 3 months for a minimum of 5 days per week and 8 hours per day.
4. Manifest cylinder ≤ 0.75 D in each eye.

8.2 Exclusion Criteria

Subjects fulfilling **any** of the following criteria are not eligible for participation in this study.

11. Wearing habitual contact lenses in an extended wear modality (routinely sleeping in lenses for at least 1 night per week) over the last 3 months prior to enrollment.

13. Monovision wearers.

16. Any habitual wear of Biofinity lenses.

Women of childbearing potential or women who are pregnant at the time of study entry are not excluded from participation. [REDACTED]

8.3 Rescreening of Subjects

Rescreening of subjects is not allowed in this study.

9 TREATMENTS ADMINISTERED

9.1 Investigational Product(s)

Test Product(s): [REDACTED] soft contact lenses

Control Product(s): [REDACTED] Biofinity (comfilcon A) soft contact lenses

Table 9–1 Test Product

Test Product	soft contact lenses (contact lens) (LID015385)
Manufacturer	Alcon Vision, LLC. [name] USA
Indication for use and intended purpose in the current study	The intended use of this contact lens is for vision correction.
Product description and parameters available for this study	
■ [REDACTED]■ [REDACTED]■ [REDACTED]■ [REDACTED]■ [REDACTED] 
■ [REDACTED]■ [REDACTED]
Usage	
• Wear:
○ Daily Wear
▪ During waking hours only.■ [REDACTED][REDACTED]○ Bilateral• Exposure: At least ~8 hours per day and ~5 days per week over a ~3 month exposure period. 
■ [REDACTED]■ [REDACTED]

[figure not shown]
	
• Lens Care: CLEAR CARE
Packaging description	Blister foil pack

Table 9–2 **Control Product**

Control Product(s)	Biofinity (comfilcon A) soft contact lenses (Biofinity contact lens) (LID010221)
Manufacturer	CooperVision
Indication for Use	The intended use of this contact lens is for vision correction.
Product description and parameters available for this study	
• Material: comfilcon A• Water content: 48%• Power range: -1.00 to -6.00 D (0.25 D steps)• Base curve: 8.6 mm (target)• Diameter: 14.0 mm (target)
Formulation	Silicone Hydrogel. Additional details can be found in the Biofinity package insert.
Usage	
• Wear:
○ Daily Wear

- During waking hours only.
 - [REDACTED]
 - [REDACTED]
 - [REDACTED]
- Bilateral
- Exposure: At least ~8 hours per day and ~5 days per week over a ~3 month exposure period.
 - [REDACTED]
 - [REDACTED]
 - [REDACTED]
 - [REDACTED]
- Lens Care: CLEAR CARE [REDACTED]
 - [REDACTED]
 - [REDACTED]
 - [REDACTED]

Packaging description	Blister foil pack.
-----------------------	--------------------

More information on the test product can be found in the IB; information on the control product can be found in the Package Insert.

9.3 Treatment Assignment / Randomization

Subjects will be randomized in a 2:1 manner to receive either the [REDACTED] or Biofinity contact lenses, respectively. [REDACTED]
[REDACTED]

Only after signing the ICF, a subject will be assigned a subject number by the electronic data capture system.

[figure not shown]
[REDACTED]
[REDACTED]
[REDACTED]
[REDACTED]

[figure not shown]
[figure not shown]
At Visit 1, all eligible subjects will be randomized [REDACTED] to one of the treatment arms. [REDACTED]
[REDACTED]
[REDACTED]
[REDACTED]

9.4 Treatment masking

This study is double-masked, with subjects randomized to use [REDACTED] or Biofinity contact lenses for the duration of the 3-month treatment period. [REDACTED]
[REDACTED]

[REDACTED]

9.5 Accountability Procedures

It is the Investigator's responsibility to ensure that:

- All study products are accounted for and not used in any unauthorized manner
- [REDACTED]

- All unused products are available for return to the Study Sponsor, as directed
- Any study lenses associated with a device deficiency or with any product-related AE (ie, ADE or SADE) are returned to the Study Sponsor for investigation, unless otherwise directed by the Sponsor. Refer to Section 11 of this protocol for additional information on the reporting of device deficiencies and AEs [REDACTED]
[REDACTED]

The Investigator is responsible for proper disposition of all unused IPs at the conclusion of the study, [REDACTED]

9.6 Changes to concomitant medications, treatments/ procedures

After the subject is enrolled into the study, the Investigator must instruct the subject to notify the study site about:

- Any new medications
- Alterations in dose or dose schedules for current medications,
- Any medical procedure or hospitalization that occurred or is planned
- Any non-drug therapies (including physical therapy and blood transfusions).

The Investigator must document this information in the subject's case history source documents.

10 STUDY PROCEDURES AND ASSESSMENTS

Subjects will be expected to attend 6 office visits, as shown below.

Visit #	Visit Type	Visit Day	[REDACTED]
Visit 1	Screening/Baseline/Randomization/Dispense	Day 1	[REDACTED]
Visit 2	Week 1 Follow-up Visit	Day 7	[REDACTED]
Visit 3	Week 2 Follow-up Visit	Day 15	[REDACTED]
Visit 4	Month 1 Follow-up Visit	Day 30	[REDACTED]
Visit 5	Month 2 Follow-up Visit	Day 60	[REDACTED]
Visit 6	Month 3 Follow-up / Exit Visit	Day 95	[REDACTED]

Country	Percentage (%)
Argentina	21.0
Australia	22.0
Austria	23.0
Belgium	23.0
Brazil	21.0
Canada	22.0
Chile	21.0
China	21.0
Costa Rica	21.0
Czech Republic	23.0
Denmark	23.0
Finland	23.0
France	23.0
Germany	23.0
Greece	21.0
Hungary	21.0
Ireland	21.0
Italy	21.0
Japan	21.0
Mexico	21.0
Netherlands	23.0
New Zealand	23.0
Norway	23.0
Portugal	21.0
Spain	21.0
Sweden	23.0
Switzerland	23.0
United Kingdom	23.0
United States	21.0

At the Screening / Baseline / Dispense Visit, study lenses will be dispensed to the subject. All subjects will wear the study lenses in a daily wear modality, only during waking hours.

Term	Percentage
GMOs	85%
Organic	80%
Natural	75%
Artificial	65%

10.1 Informed Consent and Screening

The Investigator or delegate must explain the purpose and nature of the study, and have the subject read, sign, and date the IRB/IEC-approved informed consent document. The subject must sign the ICF BEFORE any study-specific procedures or assessments can be performed, including study-specific screening procedures. Additionally, have the individual obtaining consent from the subject and a witness, if applicable, sign and date the informed consent document.

The Investigator or delegate must provide a copy of the signed document to the subject and place the original signed document in the subject's chart, or provide documentation as required by local regulations.

10.2 Description of Study Procedures and Assessments

[REDACTED] The Investigator is responsible for ensuring responsibilities for all procedures and assessments are delegated to appropriately qualified site personnel.

10.2.1 Demographics

Obtain demographic information including age, race, ethnicity, and sex.

10.2.2 Medical History and Concomitant Medications

Collect medical history information, including information on all medications used within the past 30 days. Include herbal therapies, vitamins, and all over-the-counter as well as prescription medications. Throughout the subject's participation, obtain information on any changes in medical health and/or the use of concomitant medications.

10.2.3 Investigational Product Compliance

Review subject compliance with the study lenses usage and adjunct product usage [REDACTED]

10.2.4 Adverse Event Collection: Safety Assessment

Assess and record any AEs that are observed or reported, including those associated with changes in concomitant medication dosing since the previous visit. Requirements for reporting AEs in the study can be found in Section 11.

10.2.5 Slit-Lamp Biomicroscopy: Safety Assessment

Slit-lamp examination of the cornea, iris/anterior chamber, and lens must be performed in both eyes before instillation of any diagnostic eye drops.

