11 ADVERSE EVENTS AND DEVICE DEFICIENCIES

11.1 General Information

An AE is any untoward medical occurrence, unintended disease or injury, or untoward clinical signs (including abnormal laboratory findings) in subjects, users, or other persons, whether or not related to the investigational medical device (test article). Refer to the Glossary of Terms and figures below for categories of AEs and SAEs.

Figure 11-1 Categorization of All AEs

[figure not shown]
[figure not shown]

Figure 11-2 Categorization of All SAE

SAEs

In addition to reporting all AEs (serious and non-serious) meeting the definitions, the Investigator must report any occurrence of the following as an SAE:

- An ocular infection including a presumed infectious ulcer with any of the following characteristics*:
 - Central or paracentral location
 - Penetration of Bowman's membrane
 - Infiltrates > 2 mm diameter
 - Iritis
 - Increase in intraocular pressure
 - Culture positive for microorganisms
 - Increasing size or severity at subsequent visits
- Any central or paracentral corneal event (such as neovascularization) that results in permanent opacification

- Hypopyon
- Hyphema
- Neovascularization within the central 6 mm of the cornea
- Permanent vision loss as defined by loss of 2 or more lines of BCVA from enrollment visit that fails to resolve
- Uveitis (anterior, intermediate, or posterior)
- Corneal abrasion affecting \geq 50% of corneal surface area

Significant Non-Serious AE

A significant non-serious AE is a device-related, non-sight threatening AE that warrants discontinuation of any contact lens wear for greater than or equal to 2 weeks. In addition, the Investigator must report any occurrence of the following as a Significant Non-Serious Adverse Event:

- Peripheral non-progressive non-infectious ulcers
- All symptomatic corneal infiltrative events
- Corneal staining score greater than or equal to Grade 3
- Temporary vision loss as defined by loss of 2 or more lines of BCVA from enrollment visit that persists for 2 or more weeks
- Neovascularization score greater than or equal to Grade 2

Device Deficiencies

A device deficiency is inadequacy of a medical device with respect to its identity, quality, durability, reliability, safety, or performance. A device deficiency may or may not be associated with subject harm (ie, ADE or SADE); however, not all ADEs or SADEs are due

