5.1 Safety Endpoints

The safety endpoints include the following:

- Adverse events (AE)
- Biomicroscopy Findings/Slit Lamp Examination
 - Limbal hyperemia

- Bulbar hyperemia
- Corneal staining
- Conjunctival staining
- Palpebral conjunctival observations
- Corneal epithelial edema
- Corneal stromal edema
- Corneal vascularization
- Conjunctival compression/indention
- Chemosis
- Corneal infiltrates
- Other findings
- Device deficiencies

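### Does the protocol's slit-lamp paragraph leave out most of the biomicroscopy findings that the SAP will report?

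*Protocol*

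**What the plan says.** Protocol 10.2.5 is the only visible description of the examination: "Slit-lamp examination of the cornea, iris/anterior chamber, and lens must be performed in both eyes before instillation of any diagnostic eye drops". It names no conjunctiva, limbus, dye or grading scale.

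SAP 5.1 sets out what will be reported: 11 named findings and one entry for anything else. The list includes "Limbal hyperemia", "Bulbar hyperemia", "Corneal staining", "Conjunctival staining", "Palpebral conjunctival observations" and "Corneal epithelial edema". SAP 5.3.2 has biomicroscopy at Visits 1 to 6 and at unscheduled visits, reported by eye. The schedules in Protocol Table 3-1 and SAP Table 10-1 agree and add the early exit visit.

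Protocol 11.1 makes some slit-lamp grades reportable as significant non-serious adverse events. One is "Corneal staining score greater than or equal to Grade 3"; another is a neovascularization score of Grade 2 or more.

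Protocol 12.6 and SAP 5.2 both say that there are no safety hypotheses and that the safety assessment is descriptive.

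**The concern.** Set side by side, the two lists do not match. The protocol paragraph names three sites in the eye: cornea, iris/anterior chamber and lens. The SAP list is largely about the conjunctiva and cornea, and none of its named findings concerns the iris, anterior chamber or lens. Staining is normally graded after a dye is applied, yet the only timing rule concerns what is done before drops.

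Biomicroscopy is one of three safety endpoints, and the primary objective includes safety. Sites work from the protocol, not the SAP. If some of the roughly 8 sites took 10.2.5 as the whole examination, they would record no conjunctival findings and either no staining or staining scored without dye. The by-eye summaries would then mix different examinations, and adverse events triggered by a staining grade could be missed at some sites.

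**Working it through.** No sample size, power or error rate is involved. The check is a count, followed by a reading of the passages together.

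**Count.** Each named finding in SAP 5.1 is classed by structure. It is assumed that the two staining items need a dye; neither document says so.

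| Class | Findings | Number |
|---|---|---|
| Cornea, no dye | epithelial edema, stromal edema, vascularization, infiltrates | 4 |
| Cornea, dye assumed | corneal staining | 1 |
| Limbus | limbal hyperemia | 1 |
| Conjunctiva | bulbar hyperemia, conjunctival staining, palpebral observations, compression, chemosis | 5 |

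Total: 4 + 1 + 1 + 5 = 11.

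- Strictest reading (limbus is not cornea; corneal staining is not covered because it needs a dye): 5 + 1 + 1 = 7 of 11, or 7/11 = 64%.
- One of those two accepted as covered: 6 of 11, or 6/11 = 55%.
- Both accepted (the limbus is the corneal margin, and the cornea is named): 5 of 11, or 5/11 = 45%.

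So 5 to 7 of the 11 are not described in 10.2.5, and 4 are covered on any reading.

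**Does not described mean not obtainable?** Three things say no.

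1. The sentence in 10.2.5 is a rule about order. The listed structures must be seen before drops, in both eyes. It contains no word of limitation and does not bar looking at other structures or examining again after drops. A rule about what comes before drops makes sense only if drops may be used.
2. Protocol 11.1 cannot be applied without a corneal staining grade and a neovascularization grade. Read with 10.2.5, it gives a consistent sequence: the undyed examination first, graded staining afterwards.
3. The public text is incomplete here. Section 10.2 opens with redacted text, the visible numbering goes from 10.2.6 to 10.5, and the SAP schedule has redacted rows just before and just after biomicroscopy. Dye steps or grading scales may be there. It is not known that they are, but their absence cannot be assumed.

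**The reverse mismatch.** Abnormalities of the iris, anterior chamber or lens fit the catch-all entry in SAP 5.1. Hypopyon, hyphema and uveitis are also reportable as serious adverse events under Protocol 11.1. Nothing examined is left without a place to be reported.

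**Effect on results.** No test, margin or decision rule uses these findings. The study is double-masked, so a site's way of examining should apply alike to its test and control subjects. Uneven practice could blur a descriptive comparison, but the documents give no figure from which to size that.

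**The case for a change.** The best case for a change is that 10.2.5 carries no redaction mark and reads as a complete sentence under its own heading. Even on the most lenient count, five conjunctival findings appear nowhere in the visible examination procedure, and the protocol's safety objective table says only that biomicroscopy findings are an endpoint. With no hypotheses, the safety conclusion rests on descriptive tables, which are only as good as the consistency of ascertainment across sites and six visits. Aligning the paragraph with the SAP would take a few lines and add no endpoint.

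The textual part stands: the visible paragraph is thinner than the SAP list, and the conjunctival omission is its stronger limb. What does not stand is the step to under-ascertainment. That step needs sites to treat an order-of-examination rule as a limit, to disregard a staining grade they must report under 11.1, and to have no fuller instruction in text that has been withheld. The staining limb is weaker still, because 11.1 shows the intent directly. Prescribing dye grading at every biomicroscopy visit would also go beyond what the public text establishes about when staining is done.

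**Conclusion.** No change follows. This is missing detail in one paragraph that sites and analysts can fill sensibly from the rest of the plan, not a rule that gives a wrong result. Its size is 5 to 7 of 11 named findings not described in Protocol 10.2.5, assuming that staining needs a dye and depending on how the limbus and corneal staining are classed. Sites that collect the SAP-listed findings at the planned biomicroscopy visits would still give sound descriptive safety summaries. A cross-reference between the two sections would be tidier, but it would only write down structures, order and grading that the plan already presupposes. The conclusion rests on reading 10.2.5 as a pre-drop requirement rather than a complete list, and on not counting redacted or withheld text as absent.

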10.2.6 Device Deficiencies: Safety Assessment

Assess and record any device deficiencies that are reported or observed since the previous visit. Requirements for reporting device deficiencies in the study can be found in Section 11.

10.5 Discontinued Subjects

10.5.1 Screen Failures

Screen failures are subjects who were excluded from the study after signing the informed consent, not meeting the inclusion/exclusion criteria, and prior to randomization to product/dispense of study product.

The Investigator must document the reason for screen failure in the subject's case history source documents.

Subject numbers must not be re-used.

10.5.2 Discontinuations

Discontinued subjects are individuals who voluntarily withdraw or are withdrawn from the study by the Investigator after signing the informed consent.

Subject numbers of discontinued subjects must not be re-used.

Subjects may discontinue from study or study treatment at any time for any reason. Subjects may also be discontinued from study treatment at any time if, in the opinion of the Investigator, continued treatment poses a risk to their health.

Topic	Percentage
The concept of a 'smart city'	95
Smart city technologies	85
Smart city infrastructure	80
Smart city governance	40
Smart city data	75
Smart city planning	90
Smart city implementation	95

